10.1.3 Study Enrollment

10.1.3.1 Randomization

- Infant will be randomized to one of three study arms Active-Low Dose (108 mg/kg), Active High Dose-216 mg/kg or Control-nCPAP/nIMV alone. If twins or triplets are enrolled, only the first sibling will be randomized and subsequent siblings will receive the same treatment assignment.
- Randomization is a two-step process:
 - Step 1: a designated member of the study staff will obtain a randomization envelope for the appropriate gestational age group, which will randomize the infant to either the Active or Control group. The study staff will be made aware if the infant was randomized to the control group. The randomization envelope will be stored in a secure location within the infant's study file.
 - Step 2: active envelopes will be forwarded to the unblinded pharmacist or designee, where the active envelope will be opened and the Low or High dose group (108 mg/kg or 216 mg/kg) will be determined. Active drug dose will be calculated and dispensed according to the pharmacy manual instructions. Active drug will be administered according to study protocol.

10.1.3.2 Drug Dispensing & Preparation

- Pharmacy or designee will calculate AeroFact dose (depending on group assignment) and dispense the appropriate number of trays of AeroFact to the study drug lockbox provided
- Study medication will be labeled according to the study pharmacy manual
- Study drug will not be reconstituted in the pharmacy but prepared by the unblinded respiratory therapist or designee on a just in time basis, according to package insert.
- Medication, drug calculations, additional study labels, and reconstitution instructions will be delivered to the NICU in the study drug lockbox

10.1.3.3 AeroFact Delivery System Set-up (Unblinded Staff Member Only)

- Re-usable and single patient use device components will be brought to the infant's bedside.
- See Directions for Use (DFU) Manual or the Manual of Procedures (MOP) for step by step instructions of device set-up.

10.1.4 Study Conduct

10.1.4.1 AeroFact Dosing

Patients who meet inclusion and no exclusion criteria will receive initial assigned treatment administered via nCPAP or nIMV within first twenty-four hours after birth. Up to three additional doses of AeroFact within 96 hours of birth will be allowed. Re-dosing of AeroFact will be allowed if the RSS to maintain SpO₂ between 90 and 95% is 1.5 to 2.39 and at least two hours have elapsed since the start of the previous dose:

- If FiO₂ > 0.23, re-dosing will occur.
- If FiO₂ ≤ 0.23, re-dosing is at the discretion of the investigator.

All infants randomized will be clinically managed until the criteria for treatment escalation have been met. SpO₂ between 90-95% must be used to meet study eligibility through 96 hours for all study groups (Active/Control). Site-specific SpO₂ clinical guidelines may be used after 96 hours. Each site must use these guidelines uniformly across treatment groups.

Infants will be evaluated for tolerance of AeroFact administration:

- Assess nasal congestion (none, mild, moderate, or severe) and document aspiration (nasal, oral, ETT or none) every 15 minutes during the administration of AeroFact or a minimum of 2 hours.
- Monitor oxygenation and respiratory support parameters (FiO₂, SpO₂, PEEP/CPAP pressure and flow rate, Paw, and Respiratory Support Status) every 15 minutes from the start of AeroFact dosing (T₀) until dose has been completed or a minimum of 2 hours post start of dosing.
- Dosing Tolerance Adverse Events of interest will be assessed at 4 and 24 hours after the start of each AeroFact dose.

10.1.5 Neonatal Intensive Care Unit (NICU)

Data collection will occur at the same frequency regardless of treatment assignment.

10.1.5.1 Birth to Day 28

All study infants will undergo the following procedures and evaluations:

- Monitor clinical blood gases as clinically warranted
- Infants will have oxygenation and ventilation parameters routinely monitored q 8 hours through Day 7, daily days 8 through day 28. Parameters to include: FiO₂, SpO₂, PEEP/CPAP pressure and flow rate, Paw, and Respiratory Support Status
- Assess nasal congestion (none, mild, moderate, or severe) and document aspiration (nasal, oral, ETT or none) every 15 minutes during the administration of AeroFact and/or bolus surfactant or a minimum of 2 hours.
- Evaluate dosing tolerance of AeroFact administration and/or bolus surfactant instillation
- Record AEs of interest /Co-Morbidities of Prematurity
- Record concomitant medications of interest

10.1.5.2 36 Weeks PMA

Study infants will undergo the following procedures and evaluations:

- Monitor oxygenation and respiratory support parameters (FiO₂, SpO₂, PEEP/CPAP pressure and flow rate, Paw, and Respiratory Support Status) +/- one week around 36 Weeks PMA date (Daily the week before and the week after 36 week PMA date)
- Record concomitant medications of interest
- BPD outcomes will be assessed at 36 Weeks PMA. A RAC will be performed if infant is eligible
- Record AEs of interest/Co-Morbidities of Prematurity

If an infant is discharged from the NICU prior to 36 weeks, a study member will call the family to verify respiratory support status at 36 weeks.

10.1.5.3 End of Study at 40 weeks PMA

Study infants will undergo the following procedures and evaluations:

- Monitor oxygenation and respiratory support parameters (FiO₂, SpO₂, PEEP/CPAP pressure and flow rate, Paw, and Respiratory Support Status) +/- one week around 40 Weeks PMA date (Daily the week before and the week after 40 week PMA date)
- Record concomitant medications of interest
- Record AEs/Co-Morbidities of Prematurity
- BPD outcomes will be assessed at 40 Weeks PMA. A RAC will be performed if infant is eligible

If an infant is discharged from the NICU prior to 40 weeks, a study member will call the family to verify respiratory support status at 40 weeks.

10.1.5.4 Discharge from the NICU

Study infants will undergo the following procedures and evaluations:

- Date of discharge
- Discharge disposition
- Discharge weight (grams), Recumbent Length and Head Circumference
- SpO₂
- Respiratory status
- BPD medications
- Feedings
- Audiology evaluation
- Assessment of Ophthalmology/ROP screening
- Records surgeries performed
- Record transfusions performed
- Assessment of ventilation days
- Last day on oxygen
- Last day on respiratory support
- Record concomitant medications of interest
- Discharge/End of Part I Pulmonary Questionnaire

10.2 Part II – Follow-Up

10.2.1 Follow-Up Questionnaires

Follow-Up Questionnaires will be completed by telephone with parents at 3, 6, 9, and 12 months corrected age to assess current respiratory support, the home environment, interim medical history and respiratory medical resource utilization and neurological outcomes (12 months corrected only).

11 DATA QUALITY ASSURANCE

11.1 Data Collection

Investigator(s) will enter the information required by the protocol onto the CRFs in accordance with the CRF Completion Guidelines that are provided with the CRFs. CRAs will visit each investigational site as frequently as documented in the monitoring plan to review the blinded CRFs for completeness and accuracy against the source documents. CRAs will highlight any discrepancies found in the documentation of study conduct and ensure that appropriate site personnel address the discrepancies. Only data that is blinded will be reviewed. If necessary, an unblinded CRA may visit site to review unblinded data and perform drug accountability during the course of the study. An unblinded CRA will perform drug accountability and return used and unused investigational product prior to close-out.

11.2 Clinical Data Management

Data from CRFs and other external data will be entered into a clinical database as specified in the data management plan. Quality control and data validation procedures will be applied to ensure the validity and accuracy of the clinical database. An unblinded data manager will be assigned to process the unblinded data.

11.3 Database Quality Assurance

All databases will be reviewed and checked for omissions, apparent errors, and values requiring further clarification using computerized and manual procedures. Data queries requiring clarification will be documented and returned to the investigational site for resolution. Only authorized personnel will make corrections to the clinical database, and all corrections will be documented in an audit trail.

12 STATISTICAL CONSIDERATIONS

This section presents general information about statistical considerations and concepts such as randomization, covariates, statistical power, sample size, and a brief discussion on analysis methodology, as well as some data conventions. Detailed descriptions of the statistical analysis

methods and data conventions will be included in a separate document; i.e., the Statistical Analysis Plan (SAP).

12.1 Treatment Groups

For this study the following treatment groups will be assessed:

Group	Description
Active-Low Dose	AeroFact 108 mg/kg (Aerosolized SF-RI 1)
Active-High Dose	AeroFact 216 mg/kg (Aerosolized SF-RI 1)
Control	nCPAP or nIMV alone

12.2 Description of Study Endpoints

12.2.1 Primary Efficacy Endpoint – Part I

- Proportion of infants requiring intubation/cannulation and bolus surfactant instillation in the first 7 days after birth

12.2.2 Secondary Efficacy Endpoints – Part I

- Time to first intubation/cannulation and bolus surfactant instillation between study treatments for first 7 days of life
- Compare the proportion of infants across groups receiving multiple doses of surfactant
- Number of days on mechanical ventilation from the day of birth to 40 weeks PMA or discharge.
- Number of days on supplemental oxygen administration from the day of birth to 40 weeks PMA or discharge
- Survival without bronchopulmonary dysplasia (BPD) at 36 and 40 weeks PMA

12.2.3 Additional Efficacy Endpoints – Part II

- Length of Stay (LOS) in NICU
- Assessment of pulmonary outcomes at 3, 6, 9 and 12 months corrected age
- Proportion of subjects with any respiratory resource utilization at 3, 6, 9 and 12 months corrected age
- Respiratory morbidity per quarter till 12 months of corrected age
- Assessment of modified GMFS at 12 months of corrected age

12.2.4 Safety and Tolerability Assessments

Safety and tolerability will be assessed through the monitoring of oxygenation, bradycardia, nasal congestion/aspiration (AeroFact dosing and bolus instillation of surfactant), and other adverse events (AEs) to 40 weeks PMA or discharge. Incidence of comorbidities of prematurity/AE's will be assessed. Tolerance of the AeroFact dosing administration and all doses of bolus surfactant will be assessed during and up to 24 hours following each AeroFact dose or bolus instillation. Tolerance monitoring will end and begin anew with any AeroFact dose or bolus surfactant dose administered within the 24 hour assessment period. Only SAE's resulting in death will be recorded in Part II.

12.3 Sample Size Determination and Rationale

[figure not shown]
Two hundred and sixty-one (261) subjects (87 in each arm) will be randomized in a 1:1:1 ratio in order to assure that 246 subjects (82 in each arm) complete the study. The randomization will be stratified by site, gestational age and dosing group.

Infants requiring treatment escalation in the AeroFact dose groups is estimated to be 20% and in the control group is estimated to be 40%, with an odds ratio of 0.375.

Under the above assumptions, 82 subjects in each treatment group will be required, to meet the Type I error rate of 0.05 and 80% statistical power. To accommodate the potential dropouts, a 5% dropout rate is included in this sample size calculation.

The sample size is depicted in Figure 12.1.

Figure 12-1: Sample Size

12.4 Randomization

Infants will be block randomized in a 1:1:1 partially-blind fashion to receive one of two doses of AeroFact (Active) or Control. The randomization will be stratified by site and gestational age. There will be two sets of randomization envelopes, one for each gestational age group and they will be color-coded. If twins or triplets are enrolled, only the first sibling will be randomized and subsequent siblings will receive the same treatment assignment.

Treatment group will be randomly assigned using a predetermined randomization schedule created by an independent individual who is not on the study team. The randomization schedule will be generated using an appropriate block size to help maintain treatment groups of equal size within each age strata. Subjects who do not complete the study will not be replaced.

12.5 Stratification

The randomization will be stratified by site and gestational age (26 0/7 to 28 6/7; and 29 0/7 to 31 6/7 weeks.

12.6 Blinding and prevention of Bias

For the active dose groups, clinical and research staff will remain blinded to dose level being administered. AeroFact drug delivery circuit will remain in line for the duration of dosing or a minimum of 2 hours, regardless of dose volume being administered.

Treatment unblinding for investigator site personnel will occur after the completion of Part II and all clinical data have been received, data inconsistencies have been resolved, and the database is locked, except for emergency unblinding due to safety reasons. For all other study personnel (sponsor, vendors, stats, data management, etc.), active dose unblinding will occur after the completion of Part I and all clinical data for Part I have been received, data inconsistencies have been resolved, and the database of Part I is locked, except for emergency unblinding due to safety reasons.

The control group for this study are infants treated with nCPAP or nIMV alone.

12.7 Interim Analysis (IA)

A blinded interim analysis is planned and will be conducted when approximately 60% of subjects have been randomized and completed first 7 days of life or early termination, whichever occurs first.

The main purpose of this interim analysis will be:

- sample size re-assessment to evaluate the final sample size needed to proceed with the study based on the control responder rate at interim analysis, and;
- to evaluate the safety of AeroFact primarily on the frequency of adverse events, nasal congestion/aspiration, dosing tolerance events, and serious adverse events

The results of the interim analysis are to be reviewed by an independent DSMB who would assess the data for both safety and efficacy. The DSMB responsibilities are further elaborated in the DSMB charter. The DSMB will make recommendations to the sponsor on the sample size adjustment and any safety concerns. The details of the interim analysis will be included in the statistical analysis plan.

There will be no statistical penalty or statistical adjustment due to this interim analysis as this is a blinded interim analysis with no interim unblinding.

12.8 General Statistical Considerations

All collected study data will be presented in subject data listings. Statistical analyses will be performed using SAS® for Windows, version 9.4 or later. Descriptive statistics (n, mean, standard deviation, median, minimum and maximum) will be calculated by treatment group for continuous variables. Frequencies and percentages will be presented by treatment group for categorical variables.

12.9 Analysis Populations

The details of the analysis population to be used for the study are described in the below sections.

12.9.1 Intent-to-Treat (ITT) population

The Intent-to-Treat (ITT) population is defined as all randomized subjects. The ITT population will be the primary population for the primary, secondary and additional efficacy analysis.

12.9.2 Per Protocol (PP) Population

The Per Protocol (PP) population is defined as all randomized subjects who were not associated with a major protocol violation that affects patient safety or the integrity of the data. The PP analysis of primary, secondary and additional endpoints will be considered supportive.

12.9.3 Safety Population

The Safety population is defined as all randomized subjects. This population will be used for the analysis of safety parameters.

12.10 Covariates

The covariates planned for this study will be detailed in the statistical analysis plan.

12.11 Adjustment due to Multiple Comparisons

There are two comparisons for the primary endpoint because of the two active dose groups compared with a control. Hence, a closed test procedure will be used to protect the type I error rate, the order of testing will be:

- 1) AeroFact 216 mg/kg (Aerosolized SF-RI 1) vs. Control (nCPAP or nIMV alone)
- 2) AeroFact 108 mg/kg (Aerosolized SF-RI 1) vs. Control (nCPAP or nIMV alone)

Similarly, since there are multiple secondary endpoints a closed test procedure will be used to project the Type I error rate. The order of the secondary endpoints will be specified in the statistical analysis plan.

12.12 Statistical Methods

A Statistical Analysis Plan (SAP) will be developed and approved before the database is locked. The SAP will present the detailed statistical methodology to be used in analyzing the efficacy and safety data from this trial. All inferential statistical analysis will be based on a two-sided test with a Type I error rate of 0.05.

All the efficacy analyses presented here will be conducted using both ITT and PP populations. All safety analyses will be conducted using the Safety population. All data collected will be summarized according to the variable type.

12.12.1 Subject Disposition

The disposition of all subjects who sign an ICF will be provided. The numbers of subjects screened, randomized, completed, and discontinued during the study, as well as the reasons for all post-randomization discontinuations will be summarized by treatment group. Disposition and reason for study discontinuation will also be provided as a by-subject listing.

12.12.2 Demographics and baseline characteristics analysis

Demographics and baseline characteristics will be summarized by treatment group using appropriate descriptive statistics.

12.12.3 Concomitant Medications/Therapies of Interest

Concomitant medications of interest/therapies will be summarized separately for the Safety population. All prior and concomitant medications of interest recorded in the case report form will be coded to all matching Anatomic Therapeutic Classification codes using the most recent version of WHO Drug. Descriptive summaries by treatment group will be prepared using the coded term. All concomitant medications of interest/therapies recorded in the case report form will be listed.

12.13 Efficacy Analyses

The primary analyses of the primary and secondary efficacy endpoints will be conducted on the ITT population. The PP population analyses of primary and secondary endpoints will be considered supportive.

For the efficacy endpoints the data will be summarized and compared according to the variable type:

- Continuous data summaries will include:
 - Descriptive summary of number of observations, mean, standard deviation, median, and minimum and maximum values.
 - Analysis of Covariance (ANCOVA) or Mixed Model Repeated Measures (MMRM) adjusted for stratification factors for inferential statistics.
- Categorical data summaries will include:
 - Frequency counts and percentages
 - Logit model or Generalized Estimating Equation (GEE) method adjusted for stratification factors and clustering of multiple births within a mother for inferential statistics
- Time-dependent data: Cox proportional hazards model will be used to analyze time dependent data and to depict the time to event data.

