Infants receiving active drug will continue on nCPAP/nIMV after dose completion. If oxygenation and ventilation requirements increase within 96 hours after birth, AeroFact administration may be repeated up to three times for a total of 4 doses over the first 96 hours after birth. Re-dosing of AeroFact (same randomized group) will be allowed if the RSS to maintain SpO₂ between 90 and 95% is 1.5 to 2.39 and at least two hours have elapsed since the start of the previous dose:

- If FiO₂ > 0.23, re-dosing will occur.
- If FiO₂ ≤ 0.23, re-dosing is at the discretion of the investigator.

SpO₂ between 90-95% must be used to meet study eligibility through 96 hours for all study groups (Active/Control). Site-specific SpO₂ clinical guidelines may be used after 96 hours. Each site must use these guidelines uniformly across treatment groups. All infants randomized will be clinically managed until the criteria for treatment escalation have been met. If at any time the criteria for treatment escalation are met in any of the three treatment arms, intubation and/or bolus instillation of surfactant may be administered per site's standard of care. Oxygenation, ventilation parameters, nasal congestion/aspiration and dosing tolerance will be collected for each bolus instillation of surfactant.

Criteria for treatment escalation for AeroFact or nCPAP/nIMV only therapy includes any of the following:

1. Respiratory Symptom Severity (RSS) ≥ 2.4
2. Partial Pressure of Carbon Dioxide (PCO₂) > 65 mg Hg and/or pH < 7.20
3. Base deficit > 10 mEq/L, on two blood gases 4 hours apart
4. nCPAP > 8 cm
5. Three severe apneas with bradycardia within six hours requiring escalation of support
6. Infant's work of breathing has increased warranting escalating therapy, but infant does not meet RSS or other criteria above.

Data on all enrolled infants will be assessed through 40 weeks PMA or discharge from the NICU. Information to include: maternal/infant delivery, resuscitation history, oxygenation/ventilation parameters, concomitant medications of interest, and safety. Oxygenation and ventilation mode/parameters routinely monitored q 8 hours through Day 7, daily days 8 through 28, and daily at weeks 35 to 37 and 39 to 40 PMA/discharge. If an infant is discharged from the NICU prior to 36 and/or 40 weeks, a study member will call the family to verify the respiratory support status.

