5.1 Inclusion Criteria

Preterm infants are eligible for this study if they meet all of the following criteria:

1. Parental consent obtained prior to study procedures being performed (pre-natal consent is allowed)
2. 26 0/7 to 31 6/7 weeks of gestational age
3. Weight < 2000 grams
4. Weight appropriate for gestational age (AGA 3% to 97%)
5. Age ≤ twenty-four hours at the initiation of study treatment (active or nCPAP/nIMV alone)
6. Current RSS (MAP x FiO₂) 1.4 - 2.0 (nCPAP or nIMV)
7. Chest radiograph or lung ultrasound [13,14] consistent with a diagnosis of RDS

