10.1.2 Screening (Assessment for Eligibility)

Preterm infants will be assessed for eligibility on Day 1. The following items will be assessed:

- Chest radiograph or lung ultrasound
- Gestational age and demographics (including date of birth, gender, race, and ethnicity)
- Medical history for mother and infant (including current medications)
- Birth weight, Recumbent Length, and Head Circumference
- Apgar Scores
- Respiratory support parameters (FiO₂, SpO₂, PEEP/CPAP pressure and flow rate, Paw, and Respiratory Support Status) (initial stabilization in delivery room, first stabilization in NICU, and one hour post nCPAP start)
- Qualifying RSS based on FiO₂ and CPAP calculated from parameters above
- Inclusion and exclusion criteria

The following items will be obtained prior to dosing:

- If a blood gas has been obtained for clinical purposes only, record PO₂, PCO₂, pH, bicarbonate prior to randomization/dosing, and/or as verification for meeting intubation criteria or in relationship to an SAE.
- Assess and document nasal congestion just prior to AeroFact dosing
- Evaluate identified Co-Morbidities of Prematurity prior to AeroFact dosing

If the baby has been assessed as eligible to participate in study and informed consent has been obtained, the baby may be enrolled into the study.

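### The stated primary model does not name entry RSS, a baseline value every eligible infant has; prespecifying it would be a low-cost gain in efficiency, not the repair of an error

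*Combined protocol and SAP*

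**What the plan says.** Section 12.13 sets out methods by type of variable. For categorical endpoints it gives "Logit model or Generalized Estimating Equation (GEE) method adjusted for stratification factors and clustering of multiple births within a mother for inferential statistics"; the synopsis repeats this. For time-to-event endpoints it names a Cox model and lists no covariates.

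Section 12.5 defines the stratification factors: "The randomization will be stratified by site and gestational age (26 0/7 to 28 6/7; and 29 0/7 to 31 6/7 weeks". Section 12.4 agrees. Section 12.3 differs: "The randomization will be stratified by site, gestational age and dosing group". Dosing group is the treatment itself and cannot be a baseline adjuster.

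On other covariates, section 12.10 says only "The covariates planned for this study will be detailed in the statistical analysis plan". Section 12.12 requires the SAP to be approved before database lock. The text reviewed contains no SAP beyond section 12.

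RSS enters the trial in two places that matter here:

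- **Eligibility.** Section 5.1 requires "Current RSS (MAP x FiO₂) 1.4 - 2.0 (nCPAP or nIMV", and section 10.1.2 lists among the screening items "Qualifying RSS based on FiO₂ and CPAP calculated from parameters above".
- **Escalation.** The first of six criteria in section 4.1 is "Respiratory Symptom Severity (RSS) ≥ 2.4".

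**The concern.** An infant who enters at RSS 2.0 is 0.4 below the RSS escalation line, and one who enters at 1.4 is 1.0 below it. Neither site nor a two-level gestational age captures that difference, and randomization is not stratified on it. If entry RSS predicts intubation and bolus surfactant, a model without it gives up some power and leaves any chance imbalance in severity between arms unadjusted. The value is already collected, so using it costs almost nothing.

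Timing also matters. The SAP is due only before database lock, while section 10.1.3.1 says study staff will know which infants are in the control group. A covariate list settled late could be settled when Active-versus-Control outcomes are already visible.

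**Working it through.** **1. The plan's own sample size.** Inputs from sections 12.3 and 12.12: 40% control, 20% active, two-sided alpha 0.05, power 80%, dropout 5%.

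The pooled two-proportion formula is n = [z(0.975)·√(2·p̄·q̄) + z(0.80)·√(p₁q₁ + p₂q₂)]² / (p₁ − p₂)², with p̄ = 0.30:

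- 1.960 × √0.42 = 1.270 and 0.842 × √0.40 = 0.532
- n = (1.270 + 0.532)² / 0.04 ≈ 81.2, so 82 per arm (stated: 82)
- 82 / 0.95 = 86.3, so 87 per arm and 3 × 87 = 261 in total (stated: 87 and 261)
- odds ratio = (0.20/0.80) / (0.40/0.60) = 0.375 (stated: 0.375)
- power at 82 per arm is 80.4%

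The calculation is unadjusted and takes no credit for covariates, so leaving RSS out cannot make it wrong.

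**2. What adding entry RSS could gain.** The documents give no association between entry RSS and the endpoint, so a range is assumed. Logistic regression was simulated for one dose against control, with 82 per arm, marginal rates held at 40% and 20%, and 4,000 trials per setting. Further assumptions: RSS uniform on 1.4 to 2.0 (SD = 0.6/√12 = 0.173), 40% of infants in the lower gestational-age stratum with odds ratio 2, no site term and no sibling clustering. The comparison model adjusts for the gestational-age stratum only.

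| Assumed odds ratio per SD of RSS | Power without RSS | Power with RSS | Gain (points) | Equivalent extra subjects | Conditional treatment odds ratio |
|---|---|---|---|---|---|
| 1.0 | 81.2% | 81.2% | 0.0 | 0.2% | 0.366 |
| 1.25 | 81.9% | 82.3% | 0.4 | 1.1% | 0.363 |
| 1.5 | 81.7% | 82.5% | 0.8 | 2.4% | 0.355 |
| 2.0 | 82.2% | 85.0% | 2.8 | 8.0% | 0.335 |
| 2.5 | 81.0% | 86.6% | 5.6 | 17.0% | 0.314 |
| 3.0 | 81.7% | 88.2% | 6.5 | 20.6% | 0.295 |

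Simulation error is about 0.6 points per power figure. Equivalent extra subjects is [(1.96 + z(power with)) / (1.96 + z(power without))]² − 1.

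**3. How plausible the upper rows are.** The entry range spans 0.6/0.173 = 3.46 SD. An odds ratio of 1.5 per SD therefore means 1.5^3.46 ≈ 4-fold odds between the lowest and highest eligible infants. At 2.0 per SD it is about 11-fold, and at 3.0 about 45-fold. The larger gains need a steep gradient across a narrow range.

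**4. Site.** Section 5 plans about 45 sites: 261/45 = 5.8 infants per site, and with two gestational-age strata 261/90 = 2.9 per cell. Expected events at 82 per arm are 82 × (0.40 + 0.20 + 0.20) ≈ 66. Separate indicators would need 44 site terms against about 66 events, so adjusting for site needs a stated method.

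**5. Which RSS.** Section 5.1 uses MAP × FiO₂. The abbreviation list allows CPAP or MAP. Section 10.1.2 uses FiO₂ and CPAP, from parameters recorded at three times: delivery-room stabilization, first NICU stabilization, and one hour after nCPAP starts. As written, the covariate is not uniquely defined.

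**The case against.** The strongest reply is that nothing has been omitted yet. Section 12.10 defers covariates to the SAP, sections 12 and 12.12 defer detailed methods, and 12.13 reads as a menu by variable type. This stands in part. A reader might infer that the sponsor has decided to analyse without RSS, and the documents do not show that. But 12.13 does state an adjustment set, and naming one concrete addition to it goes further than asking for the deferred list.

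A reader might also infer that offering a logit or a GEE allows an ordinary logit that ignores correlation between siblings. The text does not support this: the reference to multiple births within a mother most naturally governs both options.

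Nor do the documents show that entry RSS is a strong predictor, or the most direct one. It is one of six escalation criteria, and one of the others covers infants who do not meet the RSS threshold. After escalation, intubation or surfactant is discretionary (synopsis) or follows site standard of care (section 4.1). The entry range is narrow. All of this stands, and it is why the assumed range starts at no association.

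Finally, the simulation leaves out site and sibling clustering, so it indicates the order of the gain and does not forecast power under the full model.

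**Conclusion.** The point holds as a minor, optional improvement. The adjustment set stated in 12.13 does not name a baseline value that every eligible infant has and that lies on the same scale as an escalation criterion. The gain in power at 82 per arm is 0 to about 6.5 points over assumed odds ratios of 1.0 to 3.0 per SD, and under 1 point at 1.5 or less. These figures rest on the assumptions listed with the simulation, above all the strength of association, which the documents do not give.

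Two further inferences are tempting and wrong. The omission does not bias the comparison, because treatment is randomized. It does not undermine the 82 per arm, which is correct for an unadjusted comparison.

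Adjustment has one consequence for reporting. The planned 0.375 is a marginal odds ratio, whereas a covariate-adjusted logit estimates a conditional one (0.363 to 0.295 for RSS odds ratios of 1.25 to 3.0). A GEE averages over mothers, not over covariates, so it does not remove this difference.

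**What to change.** State the following in 12.10 and 12.13 before any by-arm data are seen. The interim analysis in 12.7 uses the control-arm rate, so this means before that analysis.

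- Keep the stratification factors and clustering on mother. Say how about 45 small sites will be handled, and reconcile the list in 12.3 with 12.4 and 12.5.
- Add entry RSS as a continuous covariate, defined as the last qualifying value before randomization, with one stated formula. Sections 5.1 and 10.1.2 and the abbreviation list must be reconciled to give it. Because ITT is all randomized subjects, add a rule for any infant without a value.
- Use the same covariates in the Cox model.
- State whether the reported odds ratio is marginal or conditional, and if marginal, how it is obtained from the adjusted model.

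The cost is wording, plus agreement on the RSS definition and the handling of site. No new data collection and no change to the sample size are needed.
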